muscle weakness), then this is the dose one above the MTD and we will not proceed with this dose or escalate the dose. The dose below the dose that generated the adverse event is the MTD. Rare but serious adverse events include second or higher degree skin burn, severe swelling, pain, ulceration, change in sensation, or muscle weakness leading to hospitalization, life-threatening events, or death.

The data safety monitoring board (DSMB) includes: [name], [name], and [name]

HF-LED-RL phototherapy and mock therapy at fluences of 480 J/cm² or 640 J/cm² will be administered to 65 subjects with Caucasian (white) skin types (Fitzpatrick skin types I, II, and III) to determine safety of HF-LED-RL at fluences of 480 J/cm² and 640 J/cm² in Fitzpatrick skin types I, II, and III. Because up to 320 J/cm² HF-LED-RL was found to be safe in all Fitzpatrick skin types (unpublished data from “previous Phase 1 LED-RL study”), this study will study 480 J/cm² and 640 J/cm² in Fitzpatrick skin types I, II, and III based on Spilker’s dose escalation protocol (X=160 J/cm², 2X=320 J/cm², 3X = 480 J/cm², and 4X = 640 J/cm²).

Number of subjects in each group:

Group 1 (480 J/cm²; 3 or 6 HF-LED-RL phototherapy subjects and 2 or 4 mock therapy subjects) - Total 5 or 10 subjects

Group 2 (640 J/cm²; 3 or 6 HF-LED-RL phototherapy subjects and 2 or 4 mock therapy subjects) - Total 5 or 10 subjects

Group 3 (480 or 640 J/cm² depending on dose escalation algorithm; 27 HF-LED-RL phototherapy subjects and 18 mock therapy subjects) - Total 45 subjects

* If there is one adverse event in one subject in either Group 1 or 2, five additional subjects will be added to that group (3 will receive HF-LED-RL and 2 will receive mock therapy).

We based our dose escalation protocol for this new study on a similar Phase 1 dose escalation study design outlined in the Journal of National Cancer Institute (Le Tourneau et al 2009), to determine dose escalation and to account for a possible outlier effect in the treatment group. Dose escalation starts at fluence of 480 J/cm² and continues up to fluence of 640 J/cm² until at least two subjects among a cohort of five to ten subjects experience an adverse event (i.e. $\geq 20\%$ of subjects with an adverse event at that dose level).

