Our dose-escalation protocol is as follows (Figure 2): In the first group (Group 1), HF-LED-RL phototherapy or mock therapy treatment time durations associated with 480 J/cm² will be administered to five subjects. Five subjects will be enrolled with three subjects randomized to HF-LED-RL phototherapy and two subjects randomized to mock therapy. Randomization is performed with website: www.randomizer.org. The randomizer will generate arabic numerals (e.g. “1”, “2,” “3”). Each enrolled subject will undergo two randomizations. For the first randomization, “1” is Group 1, “2” is “Group 2” and “3” is Group 3. 10 subjects will be

randomized to Group 1, 10 subjects will be randomized to Group 2, and 45 subjects will be randomized to Group 3. If there are no adverse events in the first five subjects of either Group 1 or 2, then the remaining 5 subjects of the 10 subjects randomized to that group will default into Group 3. For the second randomization, "1" is HF-LED-RL phototherapy and "2" is mock therapy. This study is single-blind and subjects will be blinded to this randomization, while researchers ([name], [name], and [name]) have knowledge of all subjects' randomization for the entirety of this study.

Dose escalation starts at fluence of 480 J/cm² and continues up to fluence of 640 J/cm² until at least two subjects among a cohort of five to ten subjects experience an adverse event (i.e. >20% of subjects with an adverse event at that dose level). If there are no adverse events in the five subjects treated with HF-LED-RL or mock therapy at fluence of 480 J/cm² in Group 1, then we will escalate the dose of HF-LED-RL or mock therapy to fluence of 640 J/cm² in the next cohort of five subjects (Group 2). If there is a single adverse event with HF-LED-RL or mock therapy at fluence of 480 J/cm², we will repeat the same dose of 480 J/cm² in a new cohort of five additional subjects (Group 1A). This is to account for a possible outlier effect. If two or more subjects in the first cohort of Group 1 experiences an adverse event with HF-LED-RL or mock therapy at fluence of 480 J/cm², then the study will stop and the MTD is 320 J/cm². If there are no adverse events in Group 1A, then the dose will be escalated to 640

J/cm2 in the next cohort (Group 2). If there is an adverse event in Group 1A ($\geq 20\%$), then the study will stop and the MTD is 320 J/cm2.

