After either a MTD has been established or the study endpoint of 640 J/cm2 has been achieved, an additional 27 HF-LED-RL phototherapy subjects (for a total of 30 or 33) and 18 mock therapy (for a total of 20 or 22) (determined randomly) will be enrolled to satisfy Hanley's Rule of Three, such that it can be concluded with 95% confidence that fewer than 1 person in 10 will experience an adverse event (Figure 3). (Hanley 1983) If the MTD is 320 J/cm2, then the study will be stopped and no further testing of the MTD of 320 J/cm2 in the larger cohort will be indicated because the MTD of 320 J/cm2 was already tested in a large cohort in the "previous Phase 1 LED-RL study". Of the larger expansion cohort, the study will be halted (stopped) if adverse events determined to be device related equals or exceeds 30%.

This clinical trial will be registered on <https://clinicaltrials.gov> following IRB approval and prior to subject enrollment.

- The subject will receive standard of care treatment in the dermatology clinic for any adverse event. Physical examination/visual inspection of the treated forearm will occur at every study visit. Treatment will be initiated, if indicated, for any procedural outcomes or adverse events noted at every study visit. Any general dermatology adverse events will be managed by [name] in the Dermatology clinic, per standard of care. If a skin ulcer occurs, we will record the skin ulceration as a superficial ulceration

(meaning it is nearly flush with the skin) or, if measurable, the depth of ulceration in millimeters. If skin ulceration occurs, we will consult [name], who is an expert in wound healing and head of the Sacramento VA wound clinic, for management. If change in sensation or muscle weakness occurs in a subject, the subject will be sent to Sacramento VA Emergency Room for urgent grading and management. If there are any other adverse events that cannot be managed in the Dermatology clinic, the subject will be sent to the Sacramento VA Emergency Room for urgent care.

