5.2 Recruitment Methods

- The total number of participants approved for recruitment is 200.
- Potential subjects will be identified and recruited from the Sacramento VA Medical Center, Mather via discussion with [name], [name], and/or [name] in Dermatology Clinic or through subject interest from IRB-approved flyers posted at the Sacramento VA Medical Center.
- Flyer (Please see below and as separate attachment)

Inviting Veterans to Participate in a Clinical Trial Studying the Safety of Red Light On Skin!

The Dermatology Service is exploring the safety of a FDA-cleared red light device. To study the safety of red light, we are evaluating different treatment times using the device in healthy skin over a three-week period. We previously studied the safety of light in all skin types and this study is designed to investigate the effects of light on fair skinned individuals.

Would you like to:

- Help veterans and the population at large?
- Make a contribution to medical science?
- Help discover new treatments for skin disease?
- Get compensated for your time participating in this study?

PLEASE ASK US!

Who may participate?

- Veterans of any age, with Caucasian (white) skin that may burn easily.
- Veterans who have not participated in a Sacramento VA red light study previously.
- Veterans wanting to make a positive impact on others.

Where is this study?

- Building 801, Dermatology Clinic, Sacramento VA Medical Center, Mather

If you are interested in participating in this study or if you have any questions, please contact research coordinator:

[name]
[contact]

- Subjects will receive a prorated amount of compensation based upon the number of completed study visits. Subjects must complete two or three study visits in the week to receive payment for that week. If patients complete two study visits in a week, they will receive a prorated payment of \$33.33 for that week. If a subject completes three study visits in a week, they will receive a payment of \$50 for that week. Completion of week 1: \$50, week 2: \$50, and week 3: \$50. Patients will receive a check weekly and there will be no delay in receiving the payment. If a subject misses two or more study visits total, he/she will be discontinued from the study.

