5.7 Withdrawal of Subjects

- Subjects may be withdrawn from the research without their consent in the event of an adverse event that jeopardizes the subject's safety or subject's noncompliance (e.g. missing two or more study visits). In the event that subject's study participation has to be discontinued, the principal investigator will explain to the participant the reasons for termination.
- There are no consequences/penalties should a subject decide to withdraw from the research. The subject is encouraged to contact [name] for the end-of-study visit. End-of-study visit will include photograph of the treated forearm, physical examination of the treated forearm, and collection of the subject's study diary. Subjects will be instructed to notify their primary care physician or follow-up in Dermatology clinic if any questions or concerns arise after the end of the study.

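### As far as the readable text shows, the single-event rule in Groups 1 and 2 ignores seriousness, and dosing need not wait for DSMB or IRB review after a serious event

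*Combined protocol and SAP*

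**What the plan says.** Section 5.1 applies one rule at both dose levels: "If there is one adverse event in one subject in either Group 1 or 2, five additional subjects will be added to that group". For Group 1 it is spelled out: "If there is a single adverse event with HF-LED-RL or mock therapy at fluence of 480 J/cm², we will repeat the same dose". The Abstract says the same for both groups. The stated purpose is to allow for an outlier. Any adverse event on the Section 5.1 list counts, in either arm, from a first-degree burn or erythema beyond 24 hours upward.

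After the repeat at 480 J/cm², the plan continues: "If there are no adverse events in Group 1A, then the dose will be escalated to 640" J/cm². One further event in Group 1A stops the study with the MTD set at 320 J/cm². So do two or more affected subjects in the first cohort.

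The same section describes a more severe class: "Rare but serious adverse events include second or higher degree skin burn". The list goes on to events that lead to hospitalization, threaten life or cause death. No dosing rule in the readable text refers to this class.

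Other safeguards are:
- **Checks before each session.** Subjects are asked about events, the diary is reviewed and the forearm is examined (Section 5.1 and its timeline).
- **Care of the affected subject.** For sensory change or weakness, "the subject will be sent to Sacramento VA Emergency Room for urgent grading and management". Section 5.7 adds: "Subjects may be withdrawn from the research without their consent in the event of an adverse event", where safety is at risk.
- **Reporting and oversight.** Section 6.0 gives 5 working days for reporting serious events to the IRB, and quarterly DSMB meetings.
- **A halting rule in the expansion cohort only.** "the study will be halted (stopped) if adverse events determined to be device related equals or exceeds 30" percent.

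**The concern.** A dose rule that only counts subjects treats a day and a half of redness and a life-threatening burn alike. Repeating the dose to see whether an event was an outlier is sensible for mild, reversible events. It is hard to defend as an automatic response to one serious event that the device may have caused. The MTD is defined through reversible toxicity, and no rule says what follows a single irreversible event.

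The subjects are healthy volunteers, and the doses are three and four times the cleared 160 J/cm² (480/160 = 3; 640/160 = 4). Section 2.0 reports only two subjects of skin types I to III treated at 480 J/cm² before, and a blister in the third subject treated at that dose (type V). It also says that in the previous study any adverse event ended testing at that dose. The present plan relaxes that rule and makes no exception for serious events.

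A site that follows the plan exactly could therefore go on treating, and then escalate, without the DSMB having considered the event.

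**Working it through.** The plan states no figure on this point, so there is none to reproduce. The check has two parts: whether any provision makes dosing wait, and how much exposure could follow if none does.

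**Does any provision make dosing wait?**
- Pre-session checks (Section 5.1): these come before each subject's own session. They do not hold anyone else's.
- Emergency-room referral (Section 5.1) and withdrawal (Section 5.7): these concern the affected subject only, and withdrawal is optional.
- IRB report (Section 6.0): this is a duty to inform within a time limit. Dosing is not made conditional on a response.
- DSMB (Section 6.0): it meets quarterly. No event triggers a meeting, and no cohort depends on one. The investigator may recommend protocol changes, which is discretionary.
- 30% halt (Section 5.1): expansion cohort only, so not Groups 1 and 2.

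None of these requires a completed review before other subjects' next sessions, the repeat cohort or the escalation.

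**Exposure that needs no completed review.** Inputs from Section 5.1: 3 active subjects per cohort of five; 9 sessions each, on Monday, Wednesday and Friday for three weeks.
- Repeat cohort at the same dose: 3 × 9 = up to 27 active sessions.
- Group 2 at 640 J/cm², if the 480 J/cm² repeat is clean: 3 × 9 = up to 27 active sessions, fewer if events stop dosing.
- Within the IRB reporting limit: the 5 working days after a Monday, Wednesday or Friday event always contain 3 scheduled sessions. If the other active subjects of the first cohort (at most 2) are on treatment at the same time with sessions left, that is 2 × 3 = up to 6 active sessions.

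**Timing against DSMB meetings.** Each subject has a test week and three treatment weeks, so a cohort treated concurrently takes about 4 weeks. A quarter is about 13 weeks (52/4). A prompt repeat cohort would fit between two scheduled meetings. So could the repeat followed by Group 2 (4 + 4 = 8 weeks), if recruitment were immediate. Concurrent treatment and immediate recruitment are assumptions; the plan states neither.

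**The case against.** The strongest reply is that the plan is stricter than it first looks. The repeat is deliberate. Any event in either arm counts, even erythema just over 24 hours, and a second affected subject ends the dose. Escalation needs a clean Group 1A, so at least three weeks of treatment pass after the repeat begins, and by then the IRB should have the serious-event report. The plan calls such events rare, and among the previous study's events described in Section 2.0 none is called serious. A careful investigator would probably pause anyway.

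Much of this stands, and it limits the likelihood and the number of subjects involved. It does not supply the missing step. Informing the IRB is not the same as waiting for a review, and a pause left to discretion is decided by the staff who recruit and treat the subjects.

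A reader might infer three stronger things that the documents do not support:
- *That nothing is checked before dosing.* Each subject is checked before each of their own sessions. The gap concerns the other subjects, the repeat and the escalation.
- *That the algorithm certainly has no seriousness branch.* Figure 2 is not shown. The wording of Section 5.1 has no such branch, but it also does not spell out the steps after Groups 2 and 2A, so the figure may contain more than the text.
- *That a probability, or an upper limit on one, can be given.* The documents state no serious-event rate. A calculation on active subjects alone would not be an upper limit either, because the rule also counts events under mock therapy.

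**Conclusion.** The point holds, subject to Figure 2. As written, one serious, possibly device-related event in Group 1 or 2 is handled like one mild event. It leads to five more subjects at the same dose and, after a clean repeat at 480 J/cm², to 640 J/cm², with no DSMB or IRB review required first. At stake are up to 27 active sessions in the repeat cohort and up to 27 more at 640 J/cm². These are maximum counts of permitted exposure, not expected harm. The likelihood is low if the plan's description of such events as rare is right, and it cannot be quantified from the documents. Because the consequence falls on healthy subjects and the remedy is cheap, this should be fixed before enrolment.

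**What to change.** Add a hold to the escalation rules in Section 5.1, and apply it to the expansion cohort as well.

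- **Trigger.** Any possibly device-related event that leads to hospitalization, is life-threatening, fatal or irreversible, or is a burn of second degree or worse. The trigger needs its own definition. The Section 5.1 list does not mention irreversible events, and its hospitalization clause can be read as qualifying every item, burns included.
- **Blisters.** State whether an isolated blister counts as a second-degree burn for this purpose or stays under the present counting rule. A blister is the event that set the MTD in the previous study, so the answer decides how often the hold might apply.
- **Action.** No new subject is enrolled, and no session is given at that dose or higher, until the existing DSMB has held an ad hoc review and recorded a decision to stop, repeat or continue. Events below the trigger keep the present rule.
- **Consequences for held subjects.** Section 5.2 says: "If a subject misses two or more study visits total, he/she will be discontinued from the study". Sessions missed because of a hold should not count toward this, or toward the matching noncompliance ground in Section 5.7. The DSMB decision should say whether interrupted subjects remain evaluable for escalation or are replaced.

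Section 6.0 needs a provision for ad hoc DSMB meetings. If no such event occurs, the cost is wording only. If one does, expect a short delay, perhaps an interrupted three-week course, and possibly a few replacements, for which the 200 subjects approved for recruitment leave room against the 65 planned.

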possible outlier effect. The maximally tolerated dose (MTD) will be defined as the dose level below the dose producing unacceptable but reversible adverse toxicity in two or more subjects. After either a MTD has been established or the endpoint dose of 640 J/cm² has been achieved, an additional 27 HF-LED-RL phototherapy subjects (for a total of 30 or 33) and 18 mock therapy subjects (for a total of 20 or 22), determined randomly, will be enrolled for a total of 50 subjects, such that it can be concluded with 95% confidence that fewer than 1 person in 10 will experience an adverse event.

Methods: Healthy subjects, any sex, ethnicity, and age with Fitzpatrick skin types I to III that do not meet exclusion criteria and whose nondominant proximal anterior forearm is wide enough to ensure reproducible placement of HF-LED-RL phototherapy or mock therapy hand-held unit will be recruited. Subjects with light-sensitive conditions or on photosensitizing medications, subjects with open wounds, diabetes, fibrotic skin diseases or other skin conditions affecting the nondominant proximal anterior forearm will be excluded from the study. Subjects with tattoos that cover the procedure site will also be excluded, as the tattoos may affect study findings due to altered light penetration or reflection. Subjects with Fitzpatrick skin types IV, V, and VI (darker skin phenotypes) and subjects who have participated in the "Phase 1 Study of LED-RL in Human Skin" (VA file number #15-12-00756) at the Sacramento VA Medical Center will be excluded.

Clinical Significance: The effects of visible light, while common in our environment (visible spectrum accounts for 44% of total solar energy), remain undefined. An important safety feature of visible red light (600 nm to 700 nm) is that it does not generate pro-carcinogenic DNA damage as does ultraviolet (UV) light. Recently

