- In a randomized, controlled, dose escalation Phase I study of LED-RL in Human Skin (VA file 15-12-00756) conducted by our research group (hereinafter referred to as “previous Phase 1 LED-RL study”), we studied HF-LED-RL at doses of 160 J/cm², 320 J/cm², and 480 J/cm² in all Fitzpatrick skin types. The maximum recommended starting dose (MRSD) of 160 J/cm² is based upon previously published maximum doses of LED-RL phototherapy used in clinical studies that demonstrated clinical safety with no adverse events. (Sadick 2008, Sadick 2008). In the “previous Phase 1 LED-RL study”, the MRSD (160 J/cm²) was administered to Group 1 and the dose was escalated in subsequent groups using the classical method for dose escalation as described by Spilker: starting with dose (X) increased by an equal amount (in this instance: X=160 J/cm², 2X=320 J/cm², 3X=480 J/cm², 4X=640 J/cm²). We demonstrated that the maximum tolerated dose (MTD) for HF-LED-RL was 320 J/cm² in the “previous Phase 1 LED-RL study” based on an adverse event of a blister in one male subject with Fitzpatrick skin type V with HF-LED-RL at fluence of 480 J/cm² (unpublished

data). The other two subjects, who were of Fitzpatrick skin types I to III, treated with HF-LED-RL at fluence of 480 J/cm² had no adverse event.

48 subjects had no response or adverse event to any dose of HF-LED-RL or mock therapy. Eleven subjects had an expected, anticipated adverse event: One subject had faint erythema/redness that resolved after approximately one day (less than 48 hours) and ten subjects had transient post-inflammatory hyperpigmentation (PIH), which is mild tanning.

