Three study visits per week for three consecutive weeks

[figure not shown]

Figure 3. Expansion cohort design.

- Subjects who receive HF-LED-RL phototherapy may have a greater risk compared to subjects who receive mock therapy. However, all subjects are closely monitored by [name], [name], and/or [name] three times per week for three consecutive weeks at each study visit and by review of subject's diary of adverse events. All safety precautions, including sanitizing equipment and goggles with Sani-Wipe before each study subject use, requiring subjects to use safety goggles during each session, and verifying subject identity, study procedure site of left or right forearm, and correct dose of HF-LED-RL or mock therapy, will be taken. All adverse events will be documented and if necessary, reported to the IRB.

All HF-LED-RL phototherapy and mock therapy hand-held units will be cleaned with anti-germicidal wipes before and after each procedure. All subjects' nondominant proximal anterior forearm will be cleaned with alcohol wipes prior to placement of HF-LED-RL phototherapy or mock therapy unit. All subjects will be provided with protective eyewear during all procedures. The study procedure will occur on the subject's nondominant proximal anterior forearm, with a surgical marking pen to mark three points to outline the procedure area at the start and completion of every session to ensure reproducible placement of the device. Subjects will be asked which hand is dominant or preferred when writing. Subjects can report being left-handed, right-handed, or ambidextrous. Subjects who are ambidextrous may identify their preferred nondominant forearm for the

study procedure to Principal Investigator ([name]) or study coordinators ([name] and [name]) prior to start of study.

In addition to the aforementioned precautions to minimize risks, all subjects will be screened by [name], [name], and/or [name] by reviewing their medical records and performing a physical examination after obtaining informed consent. [name], [name], and/or [name] will be present during HF-LED-RL phototherapy or mock therapy procedures, and observe and document any common expected procedure outcomes and adverse events. Any adverse event experienced by the subject will be evaluated and treated according to the standard of care.

The study subjects have direct contact information (phone numbers and email addresses) of [name], and [name] may be reached at any time.

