5.6 Data Analysis

- Once all study subjects have finished all study procedures and data collection is complete, [name], [name], and/or [name] will then be performing the data analysis. Data analysis will include analysis of demographics (e.g. age, gender, ethnicity, race, Fitzpatrick skin type) in each cohort by HF-LED-RL or mock therapy dose, frequency of adverse events by HF-LED-RL or mock therapy

groups, mean duration of erythema, total duration of erythema, and subgroup analysis by demographics of adverse events. Self-reported outcomes of erythema duration are based on self-reporting from subject's diary.

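### The conclusion of 95% confidence in fewer than 1 in 10 with an adverse event is attached to 30 or 33 HF-LED-RL subjects without its zero-event condition, and the total of 33 can arise after that condition has failed

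*Combined protocol and SAP*

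**What the plan says.** Section 5.1 (Study Design) enrols "an additional 27 HF-LED-RL phototherapy subjects (for a total of 30 or 33") once a maximum tolerated dose is set or 640 J/cm² is reached. It gives the Rule of Three as the reason and draws the conclusion "such that it can be concluded with 95% confidence that fewer than 1 person in 10 will experience an adverse event". The Abstract repeats the conclusion without naming the rule, and says that the subjects "will be enrolled for a total of 50 subjects". The visible text in neither place mentions the number of events observed, the sidedness of the limit, or the arm and dose that form the denominator.

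The second figure, 33, comes from the repeat-cohort rule in section 5.1. After one adverse event in Group 1 or 2, "five additional subjects will be added to that group (3 will receive HF-LED-RL and 2 will receive mock therapy"). The event may be in either arm.

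The plan allows events during the expansion: "the study will be halted (stopped) if adverse events determined to be device related equals or exceeds 30" per cent. Section 5.6 (Data Analysis) plans the "frequency of adverse events by HF-LED-RL or mock therapy" group, with no confidence limit.

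**The concern.** This is the stated basis for the expansion size, and the only conclusion in the visible text that carries a confidence level. Safety is the trial's sole objective, and section 2.0 says that later phase II studies may rely on these safety data. As worded, the conclusion follows from enrolment, when it depends on what is observed. One event among HF-LED-RL subjects removes it. The same conclusion is also attached to 33, a total that may exist because such an event has already happened. The visible text does not say what will be concluded in that case.

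**Working it through.** **Inputs**

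- Confidence 95%, rate to exclude 0.10, and HF-LED-RL totals of 30 (27 + 3) or 33 (27 + 6): section 5.1.
- Cohorts of 3 HF-LED-RL and 2 mock subjects: section 5.1.
- Subjects missing two or more visits are discontinued (section 5.2) or may be withdrawn (section 5.7). No dropout allowance is stated.
- Assumption: the rate of interest is that of HF-LED-RL subjects at the expansion dose, with escalation and expansion subjects combined. The plan's own 27 + 3 and 27 + 6 imply this.

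**1. The plan's figure.** Rule of Three: n = 3/0.10 = 30. Exact check: the smallest n with 0.9^n ≤ 0.05 is ln(0.05)/ln(0.9) = 28.4, so 29. The figure of 30 reproduces.

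**2. Exact 95% upper limits (Clopper-Pearson).** With no events the one-sided limit is 1 − 0.05^(1/n). With one event it is the value U that solves (1 − U)^n + nU(1 − U)^(n−1) = 0.05.

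| Events/n | One-sided 95% upper limit | Below 10%? |
|---|---|---|
| 0/28 | 10.15% | no |
| 0/29 | 9.81% | yes |
| 0/30 | 9.50% | yes |
| 0/33 | 8.68% | yes |
| 1/30 | 14.86% | no |
| 1/33 | 13.59% | no |
| 1/36 | 12.51% | no |

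With one event, the smallest n that gives a limit below 10% is 46 (1/46 = 9.90%; 1/45 = 10.11%). With no events, losing two of 30 to non-evaluability is enough to lose the conclusion. A two-sided 95% interval, 1 − 0.025^(1/n), gives 11.6% for 0/30 and 10.6% for 0/33, so sidedness has to be stated.

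**3. How 33 arises under the fixed counts.** Group 3 has 27 HF-LED-RL subjects. The expansion dose contributes 3 more, or 6 if its cohort was repeated. Repetition requires one event among the first five subjects at that dose.

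- Event in an HF-LED-RL subject: the best attainable result is 1/33, with a limit of 13.6%.
- Event in a mock subject: 0/33 is still attainable, with a limit of 8.7%.

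If both arms have the same risk (an assumption), the event is in an HF-LED-RL subject with probability 3/5 = 60%. It is more if HF-LED-RL is riskier. Section 5.1 allows for that without asserting it: "Subjects who receive HF-LED-RL phototherapy may have a greater risk compared to subjects who receive mock therapy".

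**4. How 33 arises under the default rule.** Section 5.1 also allocates 10, 10 and 45 subjects to Groups 1 to 3, and moves the unused five of an event-free group into Group 3. The sums below assume a 3:2 split, and that unused Group 2 subjects do not move after Group 2 events.

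| Expansion dose | Earlier course | HF-LED-RL at that dose |
|---|---|---|
| 480 J/cm² | Group 1 event-free | 27 + 3 + 3 = 33 |
| 480 J/cm² | Group 1 repeated | 27 + 6 = 33 |
| 640 J/cm² | only Group 1 repeated | 27 + 3 + 3 = 33 |
| 640 J/cm² | both repeated | 27 + 6 = 33 |
| 640 J/cm² | both event-free | 27 + 3 + 3 + 3 = 36 |
| 640 J/cm² | only Group 2 repeated | 27 + 3 + 6 = 36 |

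On the first and third rows, 33 arises with no event at the expansion dose.

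**5. Chance of at least one HF-LED-RL event, 1 − (1 − p)^n, at assumed true rates.**

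| p | n = 30 | n = 33 |
|---|---|---|
| 1% | 26.0% | 28.2% |
| 2% | 45.5% | 48.7% |
| 5% | 78.5% | 81.6% |

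**6. Totals.** 30 + 20 = 50 matches the Abstract. The Abstract's other pair, 33 + 22, gives 55. Section 5.1 gives 10 + 10 + 45 = 65.

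**The case against.** The strongest reply is that the Rule of Three is by definition a zero-event rule. Section 5.1 names it, and the title of the cited reference concerns zero numerators. Read as a sizing rationale, the sentence is conventional and its number is right. That stands for 30. It does not rescue 33, where the rule is invoked on a path that may already contain an HF-LED-RL event. The Abstract does not name the rule at all.

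It can also be said that no escalation, maximum-tolerated-dose or halting rule uses this limit, and that anyone could compute it from the frequencies in section 5.6. Both are true. The effect is on what the trial will claim, not on how it is run. But a limit left for the reader to compute does not correct a conclusion already stated in the plan.

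Three stronger readings are tempting, and the documents do not support them:

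- *The sample size is wrong.* It is not: 30 exceeds the exact minimum of 29.
- *A total of 33 always means that the conclusion has failed.* The triggering event may be in a mock subject, and under the default rule 33 can arise without any event at the expansion dose.
- *The previous study shows that zero events is implausible.* Section 2.0 does report that "Eleven subjects had an expected, anticipated adverse event", but ten of these had transient hyperpigmentation, which section 5.1's list of events does not name. The results also mix mock therapy, doses and skin types, so they give no usable rate for types I to III at 480 or 640 J/cm².

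**Conclusion.** The point holds and should be fixed. The plan states a property that the design has only under conditions the visible text omits: no HF-LED-RL event at the expansion dose, at least 29 evaluable HF-LED-RL subjects, and a one-sided limit. One event moves the limit from 9.5% to 14.9% at 30 subjects, and from 8.7% to 13.6% at 33.

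The limits rest on HF-LED-RL subjects at one dose as the denominator. The link between 33 and a prior event rests on the fixed group sizes, which conflict with the default rule in the same section. The event probabilities rest on assumed rates. Figures 2 and 3 are not shown, so any wording inside them could not be checked.

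**What to change.** 1. In the Abstract and section 5.1, state that the below-10% conclusion is drawn only if no HF-LED-RL subject at the expansion dose has an adverse event and at least 29 such subjects are evaluable (exact one-sided 95% upper limits: 0/29 = 9.8%, 0/30 = 9.5%, 0/33 = 8.7%; 0/28 = 10.15% does not suffice). Otherwise, report the exact one-sided 95% upper limit for the observed count and the actual evaluable denominator, and do not draw the conclusion.
2. Say there which events count for this limit: any adverse event or device-related events only, and whether transient hyperpigmentation is included.
3. Add the limit, for the HF-LED-RL arm at the expansion dose, to section 5.6.
4. Secondary: reconcile the totals of 50, 55 and 65, and the fixed Group 3 size with the default-into-Group-3 rule, so that the denominator is known.

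The cost is wording and one added line of analysis, with no extra subjects. The downside is a less favourable conclusion whenever an HF-LED-RL event occurs: at an assumed true rate of 2%, about 45% of trials with 30 such subjects, and about 49% with 33, could not claim a rate below 10%.
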